#### 19.5.1. VITAL SIGNS SPECIFIC DERIVATIONS

• Temperature ( ${}^{0}$ C) = (5/9) (Temperature ( ${}^{0}$ F) – 32)

## 19.6. PHYSICAL EXAMINATION

All physical examination assessments will be listed.

## 20. PHARMACOKINETICS ANALYSIS

The PK analyses for the Main Study are described in the subsequent paragraphs. All PK concentrations will be reported and analyzed with the same precision as the source data provided by the bio-analytical laboratory regardless of how many significant figures or decimals the data carry. The unrounded derived PK parameters will be considered the source data for the calculation of descriptive statistics and rounded for reporting purposes in bysubject listings. Pharmacokinetic parameters will be listed with the following rounding/precision conventions:

- Parameters directly obtained from source data (e.g., Cmax, dose-normalized Cmax, and Ctrough) will be reported and analyzed with the same precision as the source concentration data.
- Parameters obtained from actual elapsed sample collection times (e.g., tmax) will be reported with the same precision as the actual elapsed sampling time value (2 decimal places) of the source data.
- All other pharmacokinetic parameters will be listed to one significant figure greater than precision of bioanalytical data

Summary statistics for PK concentrations will include: number of observations (n), mean, SD, coefficient of variation (CV%), geometric mean, geometric CV%, minimum, median, and maximum.

[figure not shown]
Summary statistics for PK parameters, except  $t_{max}$ , will include: n, arithmetic mean, arithmetic SD, CV%, minimum, median, maximum, geometric mean, and geometric CV%; geometric mean and geometric CV% will be calculated from available individual values that are greater than 0. For geometric mean calculation, the mean of log transformed values will be calculated, and then transformed back to the original scale by exponentiation.

The PK parameter tmax will be summarized using n, median, minimum, and maximum.

An  $n \ge 3$  will be required for calculations of descriptive statistics. If n < 3, no descriptive statistics will be calculated; only n, minimum, and maximum, will be presented.

For the reporting of descriptive statistics, the mean, SD, geometric mean, and geometric CV% will be presented to one digit more precision than rounding of the source data. The minimum, median, and maximum will be presented to the same precision as rounding of the source data. Coefficient of variation will always be reported to 1 decimal place.

### 20.1. PLASMA CONCENTRATION DATA

Plasma concentrations of each analyte will be summarized at the scheduled visit by scheduled time (where applicable) and stratified by formulation and treatment. Summaries for overall treatment group will also be presented.

Concentrations that are BLQ will be treated as missing for the computation of geometric descriptive statistics, and zero for the computation of the remaining descriptive statistics. Concentrations that are missing will be omitted from the calculation of descriptive statistics. Concentrations associated with sampling time deviations will be included in the summaries, providing:

- For pre-dose timepoint, the samples are collected before the next dose,
- For post-dose timepoints, the samples are collected after the previous scheduled time

and before the next scheduled time, and the time deviation is not significant, as adjudicated by PK scientist and clinical pharmacologist (in which case their time deviance and its adjudication will be noted in protocol deviations).

Only samples collected on Day 1 will be included in the Day 1 summaries (i.e., 0 day for the time window). For the summaries of visits after Day 1, under assumption for steady-state, samples collected on a day outside of the time window of  $\pm 3$  days allowed in the protocol will still be included in the summaries for the corresponding scheduled visit.

For each PK analyte, figures of arithmetic mean (SD) concentration-time serial profiles overlaid by treatment group, by dosage form and overall will be presented for Day 1, Day 2, and Week 4. By-subject plots of concentration-time serial profiles, overlaying parent and all metabolites will also be presented for Day 1, Day 2, and Week 4, with the 3 assessment days represented as panels in a single plot. All concentration-time profiles will be depicted on linear and semi-logarithmic scales.

Additional data presentation of pre-dose (Ctrough) concentrations is described in Section 20.2.

## 20.2. PLASMA PHARMACOKINETIC PARAMETERS

Plasma PK parameters for olorinab and the metabolites and after the first dose of the corresponding day on Day 1, Day 2, and at Week 4 will be calculated by noncompartmental methods. Actual elapsed time from dosing will be used. The following data handling conventions apply to the PK analyses for all analytes on Day 1, Day 2, and at Week 4, unless otherwise indicated:

- Pre-dose samples that are BLQ will be assigned a numerical value of zero.
- Any pre-dose concentration values that are quantifiable on Day 1 will be included in the PK analysis and identified in the CSR and the subject will be considered for potential exclusion from the pharmacokinetic analysis set. Although quantifiable concentration values at pre-dose on Day 1 are considered as anomalous, the PK parameters shall be listed and included in the parameter summaries for all such cases as a conservative approach to retain data for the study in patient population.
- Missing pre-dose samples:
  - On Day 1, will be assigned a numerical value of zero and the subject will be considered for potential exclusion from the pharmacokinetic analysis set,
  - On Day 2 and at Week 4, will be kept as missing and Ctrough will not be calculated.
- Post-dose BLQ concentrations will be assigned a value of zero if they precede quantifiable data points in the initial portion of the profile.

Page 60 of 77

- A BLQ value that occurs between quantifiable data points prior to Cmax, will be assigned concentration of zero.
- Following Cmax, BLQ values embedded between 2 quantifiable data points will be treated as missing.
- Trailing BLQ values after the last quantifiable concentration will be set to zero.

In addition, for calculating Day 1 AUC(0-8):

- Actual time of sample collection, regardless of time deviations, rather than scheduled time shall be used to derive AUC0-8.
- If concentration at t=8 h is available but collection time is missing, AUC(0-8) will be calculated using scheduled time.
- If concentration at t=8 h is missing, AUC(0-8) will not be calculated
- AUCall shall be used as an estimate of AUC(0-8) if concentrations fall to BLQ at or before reaching t=8 h.

The same nominal dose administered will be used for both the powder in capsule (PIC) and tablet formulations (as the dose input for the olorinab analysis and for calculating dose-normalized exposures for the different analytes).

The following PK parameter	s will be calculated for olorinab and the metabolites	
	unless otherwise indicated:	

Page 61 of 77

Ctrough Observed plasma concentration at the end of the dosing interval, obtained from the value

measured prior to the next dose.

(Unit: ng/mL).

Cmax Maximum concentration in plasma

(Unit: ng/mL).

 $C_{max}/D$  Dose-normalized  $C_{max}$ .

(Unit: ng/mL/mg).

tmax Time of maximum concentration

(Unit: h).

MRCmax Molar-corrected metabolite to parent (olorinab) Cmax ratio ,calculated as follows:

 $\frac{\text{metabolite Cmax}}{\text{olorinab Cmax}} \times \frac{\text{olorinab MW}}{\text{metabolite MW}}$ 

MRCmax will be calculated for and

AUC(0-8) Area under the concentration-time curve of the analyte in plasma during the dosing

interval.

(Unit: ng\*h/mL)

AUC(0-8)/D Dose-normalized AUC(0-8)

(Unit: ng\*h/mL/mg).

 $MRAUC_{(0-8)}$  Molar-corrected metabolite to parent (olorinab)  $AUC_{(0-8)}$  ratio, calculated as follows:

 $\frac{\text{metabolite AUC}(0-8)}{\text{olorinab AUC}(0-8)} \times \frac{\text{olorinab MW}}{\text{metabolite MW}}$ 

MRAUC(0-8) will be calculated for

The areas under the curve will be calculated by linear up/log down trapezoidal summation, where at least 3 quantifiable post-dose concentrations are available.

The parameter Ctrough will be obtained from concentrations measured pre-dose at Weeks 2, 4, 8, 10, and 12. Other parameters (Cmax, Cmax/D, tmax and MRCmax) will be calculated for Day 1, Day 2 (protocol Amendment 1 only), and Week 4. In addition, for subjects who are randomized under protocol Amendment 1 with more timepoints in the PK sampling schemes, Ctrough obtained from concentrations measured at 8-hour timepoint on Day 1 and pre-dose on Day 2, and AUC(0-8) and MRAUC(0-8) on Day 1 will also be calculated.

Individual plasma PK parameters will be listed and summarized for each analyte at the scheduled visit and by treatment, formulation, and IBS subtype. Day 1 PK parameters will be summarized separately for subjects who are randomized under protocol Amendment 1 and after protocol Amendment 1. In the event that subject numbers are too low to summarize Day 1 PK parameters by treatment, formulation, and IBS subtype (less than 3 subjects in each subgroup), parameters may be summarized by treatment and formulation, and additionally by treatment and IBS subtype.

Ctrough of each analyte will be summarized per day, treatment, formulation, and IBS subtype, for all pre-dose trough concentrations sampled within the following time brackets: 12 hours of the previous day's dose (immediate prior dose was not more than 12 hours before trough sample) and within one hour of dosing (trough sample taken at or not more than one hour before) on the trough assessment day. Summaries for overall treatment group will also be presented. For each analyte, figures of geometric mean (geometric CV%) Ctrough profiles overlaid by treatment group will be presented on linear scales. Individual values and geometric means of Cmax will be plotted versus dose for Day 1, Day 2, and at Week 4. In addition, plots of individual values and geometric means of AUC(0-8) versus dose on Day 1 will be presented for the overall treatment group of subjects who are randomized under protocol amendment 1.

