- Pharmacokinetic blood samples will be collected on Day 1 prior to and 0.5, 1, 2, 4, and 8 hours after the first dose of study treatment and 10 hours after the first dose of study treatment (2 hours after second dose). Additional samples will be collected on Day 2, prior to the first daily dose of study treatment and 2 and 4 hours after the first daily dose.

The PK sampling schemes specified in protocol amendment 2 and protocol amendment 3 (Main Study) include the following timepoints:

• Pharmacokinetic blood samples will be collected at study visits at Weeks 2 (Visit 4) through 10 (Visit 7) prior to the first daily dose. Blood samples will also be collected at Weeks 12 and 14 during the scheduled study visit. At Week 4 (Visit 5), in addition to samples collected prior to the first daily dose of study treatment, blood samples will be drawn 0.5, 1, and 2 hours after the first daily dose of study treatment administered at the clinic during the study visit. If a subject discontinues the study, a final PK sample will be collected at the Early Termination visit.

Pharmacokinetic blood samples will be collected on Day 1 prior to the administration of study treatment and 0.5, 1, and 2 hours after the administration of study treatment.

[figure not shown]

Figure 1: Schematic Diagram of Main Study Design

Notes: The Screening Period may be extended to up to a total of 4 weeks for subjects who consent to colonic biopsy. The last day of the Run-in Period is Day -1 and the first day of the Main Study Treatment Period is Day 1. There is not a designated Day 0 in this study. For subjects randomized under protocol amendment 1, there was an overnight observation period following randomization on Day 1, with orthostatic vital sign (VS) and 12-lead electrocardiogram (ECG) measured at multiple timepoints. See orthostatic VS and ECG analyses under Safety Section for details.

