#### 17.1. DERIVATIONS

Compliance to study treatment is based on the Drug Accountability eCRF and will be calculated as the number of capsules/tablets taken (total dispensed – total returned) divided

by the prescribed number of capsules/tablets, expressed as a percentage (see calculations below).

The study treatment is given three times daily (tid), and it is assumed that the subject should take study treatment from the morning of the visit day at which their treatment is initially dispensed to the evening before their last treatment return date, as subjects are advised to wait to take their dose at the study site until all assessments and procedures have been completed on study days. For example, if the initial dispensation date is Day 1 and the last return date is Day 85, then the subject should have taken 3 capsules/tablets each day on Days 1 to 84; hence, the total number of prescribed capsules would be  $84 \times 3 = 252$ . Multiple bottles may be dispensed at one visit; in these cases, "Per Visit" compliance will be nonmissing if at least one bottle is returned.

• "Per Visit" Compliance to study treatment at Visit X will be calculated as follows:

```
\frac{([\text{N of Capsules dispensed at Visit }(X)] - [\text{N of Capsules returned at Visit }X+1])}{\{[\text{Date of Visit }X+1] - [\text{Date of Dispensing at Visit }(X)]\} \times 3} \times 100
```

• Overall Compliance to study treatment will be calculated as follows:

For subjects who permanently stop the study treatment before Week 12, the "Date of Visit X" in Overall Compliance calculations will be replaced by the date of study withdrawal.

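### Read literally, the one-hour trough rule in SAP 20.2 would leave Week 12, a planned trough visit, out of the Ctrough summaries and figures

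*SAP*

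**What the plan says.** All SAP references are to the Main Study SAP.

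- **Planned trough visits (SAP 20.2).** Ctrough "will be obtained from concentrations measured pre-dose at Weeks 2, 4, 8, 10, and 12". Subjects randomized under Amendment 1 also have troughs on Day 1 and Day 2.
- **Which troughs are summarised (SAP 20.2).** Ctrough is summarised "for all pre-dose trough concentrations sampled within the following time brackets". Two brackets follow, joined by *and*. The first concerns the previous day's dose: "immediate prior dose was not more than 12 hours before trough sample". The second is "within one hour of dosing (trough sample taken at or not more than one hour before) on the trough assessment day". No visit is excepted. The geometric-mean Ctrough figures are specified in the same paragraph.
- **Sampling (SAP 4.1, scheme for Amendments 2 and 3).** "Pharmacokinetic blood samples will be collected at study visits at Weeks 2 (Visit 4) through 10 (Visit 7) prior to the first daily dose". The next sentence reads: "Blood samples will also be collected at Weeks 12 and 14 during the scheduled study visit". The Amendment 1 scheme draws the same distinction.
- **End of dosing (SAP 17.1).** For compliance, subjects are assumed to take treatment "to the evening before their last treatment return date". The worked case is "if the initial dispensation date is Day 1 and the last return date is Day 85", which gives dosing on Days 1 to 84 and 252 units.

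**The concern.** The second bracket can be met only if a dose follows the sample on the same day. If the Week 12 visit has no such dose, no Week 12 sample can qualify, although Week 12 is on the SAP's own list of trough visits. This is more than missing detail: a stated rule, applied as written, empties a summary that the SAP plans.

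Ctrough is one of the PK parameters named among the secondary endpoints (protocol 8.3.1.1). Week 12 is the last planned trough and the visit of the primary endpoint. Whoever programs the tables would have to leave the Week 12 row and figure point empty or depart from the SAP without a rule to cite.

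**Working it through.** **1. Reproduce the SAP's figure.** Prescribed units = (return day − dispensing day) × 3 = (85 − 1) × 3 = 252, as SAP 17.1 states. One further dose on the return day would give 253. The convention therefore counts no dose on Day 85.

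**2. Is the last return the Week 12 visit?** Protocol 5.6 has compliance assessed from returned drug at Visits 4 to 8, and protocol 3.8 identifies Visit 8 as Week 12. Because the convention runs from the return date, the ± 3 day window in protocol 3.6 does not alter the result:

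| Week 12 visit on | Last counted dosing day | Units |
|---|---|---|
| Day 82 | 81 | 81 × 3 = 243 |
| Day 85 | 84 | 84 × 3 = 252 |
| Day 88 | 87 | 87 × 3 = 261 |

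**3. Set this beside other text.** SAP 4.1 describes the Week 2 to 10 samples by reference to a dose. It groups Week 12 with Week 14, a follow-up visit after treatment has ended, and mentions no dose. SAP 7.2 builds the 12 treatment weeks as 7-day blocks from Day 1 (12 × 7 = 84 days) and starts follow-up Week 13 on the day after the last dose, which fits a last dose on Day 84. Protocol 5.10 provides no further treatment after the Treatment Period to subjects who take part only in the Main Study.

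**4. Apply the brackets.** Let p be the hours from the prior dose to the sample, and n the hours from the sample to the next dose that day. A trough is kept if p ≤ 12 and 0 ≤ n ≤ 1. At Weeks 2 to 10, n exists and both conditions can hold. At a visit with no later dose, n does not exist, so the second condition fails for every value of p.

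**5. Illustration with assumed times.** The documents give no clock times. I assumed a last evening dose at 19:00, 20:00, 21:00, 22:00 or 23:00, a sample at 07:00, 08:00, 09:00, 10:00 or 11:00, and, where a dose follows, a gap of 0.25, 0.5, 1 or 1.5 hours (5 × 5 × 4 = 100 combinations).

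| Visit | Both brackets | 12-hour bracket only |
|---|---|---|
| Weeks 2, 4, 8, 10 (dose follows) | 45 of 100 | 60 of 100 |
| Week 12 (no dose follows) | 0 of 100 | 60 of 100 |

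Only the zero is independent of the assumed times. The other counts show how the rule works and are not forecasts.

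**6. Size.** One of the five trough visits common to all subjects is affected. The planned active-treated total is 3 × 60 = 180 (SAP 8). That is a ceiling: it allows for no dropout or missing samples, and it assumes every sample meets the 12-hour bracket.

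**The case against.** The strongest reply is that the key fact is not visible. Whether a clinic dose is given at Week 12 belongs in the schedule of assessments or in protocol 5.1, and neither can be read here. Some visible text suggests such a dose:

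- SAP 20.2 itself calls the Week 12 sample pre-dose.
- SAP 16 takes the date of last administration from the on-site dosing form.
- Protocol 4.4.1 has subjects hold the morning dose until after fasted blood draws and makes no exception for Week 12.
- Protocol 3.6 lists Visit 8 among the Treatment Period visits.

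SAP 17.1 is also a compliance convention, introduced as an assumption with an example. It is not a dosing instruction, and reproducing 252 confirms only the accounting.

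This stands as a limit on certainty. None of these statements provides for a Week 12 dose, and the pre-dose label is one side of the conflict. A reader might infer that the documents prove there is no Week 12 dose, but they support only an inference.

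A reader might also infer that the Week 12 trough data are thrown away. They are not: SAP 20.2 lists individual PK parameters without the brackets, and SAP 20.1 summarises concentrations by scheduled visit, requiring of off-time pre-dose samples only that they precede the next dose. Nor can one say that a planned analysis relating Week 12 exposure to Week 12 pain is lost, since no visible text plans one. Troughs at Weeks 2, 4, 8 and 10 remain.

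**Conclusion.** The point holds as an internal conflict in the SAP. On the visible text, the second bracket cannot be met at Week 12, so the Week 12 Ctrough summary and its point in the Ctrough figures would be empty. That is 1 of 5 planned trough visits and at most 180 subjects.

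The conclusion assumes that no dose follows the Week 12 sample on the visit day and that the brackets are applied as written, with both required. The first assumption deserves medium confidence until the schedule is checked. A subject who did take a dose within the hour after sampling would be kept, but the visible plan provides no such dose. The matter is minor: listings and concentration summaries survive, and no efficacy or safety result depends on it.

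**What to change.** 1. Reconcile the pre-dose label for Week 12 in SAP 20.2 with the sampling text in SAP 4.1 and the dosing convention in SAP 17.1, stating whether a dose follows the Week 12 sample. If the schedule already provides for one, saying so resolves the conflict and the brackets can stay as they are.
2. Add to SAP 20.2 that, where no dose follows the sample on the assessment day, only the first bracket applies: the immediate prior dose was taken on the previous day, no more than 12 hours before the sample, and no dose was taken that day before sampling. The last condition matters, because otherwise a sample drawn soon after a dose at home could be summarised as a trough.
3. Keep both brackets for Weeks 2 to 10.

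The cost is one SAP clause and a check of the schedule. The 12-hour bracket already needs the time of the prior dose, so the clause calls for no further dosing or sampling times.

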### 21. IMPACT OF COVID-19

The study has been closely monitored during the period of COVID-19 and the impact of COVID-19 to data analyses is minimal. The below analyses related to COVID-19 are planned to document any impacts of the pandemic. Post hoc explanatory data analyses may be planned after database lock if the data warrants the request.

- Summary of major protocol deviations caused by COVID-19
- A listing of any adverse events related to COVID-19
- A listing of any subjects with phone or remote visits due to COVID-19.

### 22. GENETIC AND BIOMARKERANALYSES

Genetic and biomarker analyses will be completed by Sponsor and will be described in a separate analysis plan if needed.

### 23. DATA NOT SUMMARIZED OR PRESENTED

The other variables and/or domains not summarized or presented are:

Page 63 of 77

- Comments
- Meals (Day 1)

These domains and/or variables will not be summarized or presented but will be available in the clinical study database, SDTM and/or ADaM datasets.

# 26. APPENDIX 2. PARTIAL DATE CONVENTIONS

Imputed dates will NOT be presented in the listings.

# **ALGORITHM FOR TREATMENT EMERGENCE OF ADVERSE EVENTS:**

AE START DATE	AE STOP DATE	ACTION
Known	Known, Partial or Missing	If AE start date < study treatment first dose date, then not TEAE  If AE start date ≥ study treatment first dose date, then TEAE
Partial, but known components show that it cannot be on or after date of first dose of study treatment	Known, Partial or Missing	Not TEAE
Partial, could be on or after date of first dose of study treatment	Known	If AE stop date < study treatment first dose date, then not TEAE  If AE stop date ≥ study treatment first dose date, then TEAE
	Partial	Impute AE stop date as latest possible date (i.e. last day of month if day unknown or 31st December if day and month are unknown), then:  If AE stop date < study treatment first dose date, then not TEAE  If AE stop date ≥ study treatment first dose date, then TEAE
	Missing	Assumed TEAE

Page 68 of 77

AE START	AE STOP	ACTION
DATE	DATE	
Missing	Known	If AE stop date < study treatment first dose date, then not TEAE  If AE stop date ≥ study treatment first dose date, then TEAE
	Partial	Impute AE stop date as latest possible date (i.e. last day of month if day unknown or 31st December if day and month are unknown), then:  If AE stop date < study treatment first dose date, then not TEAE  If AE stop date ≥ study treatment first dose date, then TEAE
	Missing	Assumed TEAE

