#### 8.3.4.1. Adverse Events

AEs will be coded using Medical Dictionary for Regulatory Activities (MedDRA).

For each treatment group, the proportion of subjects with TEAEs will be summarized overall, by severity, and by relationship to olorinab. A TEAE is defined as:

- An AE that occurs after initiation of olorinab that was not present at the time of treatment start.
- An AE that increases in severity after the initiation of olorinab, if the event was present at the time of treatment start.

Incidence of AEs, SAEs, and TEAEs leading to study treatment discontinuation will be summarized and presented in descending order of frequency. AEs occurring before the first dose of olorinab will be summarized separately.

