### 19.1. ADVERSE EVENTS

AEs will be coded using Medical Dictionary for Regulatory Activities (MedDRA) central coding dictionary, Version 23.0 or higher. Treatment-emergent adverse events (TEAEs) are defined as:

- An AE that occurs after the first dose of study treatment (olorinab or placebo) that was not present before the first dose of treatment, OR
- An AE that increases in severity after the first dose of study treatment (olorinab or placebo), if the event was present before the first dose of treatment.

All TEAEs will be coded and summarized by system organ class (SOC) and preferred term (PT) and will be presented by descending order of frequency. AEs occurring before the first dose of study treatment will be summarized separately. Listings will include all AEs (TEAEs and Non-TEAEs).

See Appendix 2. Partial Date Conventions for handling of partial dates for AEs for the purpose of assigning treatment-emergent flags. In the case where it is not possible to define an AE as treatment-emergent or not, the AE will be classified by the worst case; i.e. treatment emergent.

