## 18.1. ADVERSE EVENTS

AEs will be coded using MedDRA central coding dictionary, Version 23.0 or higher. New treatment-emergent adverse events (TEAEs) in LTE are defined as:

- An AE that occurs after the first dose of LTE study treatment that was not present before the dosing, OR
- An AE that increases in severity after the first dose of LTE study treatment if the event was present before the dosing treatment.

All TEAEs will be coded and summarized by system organ class (SOC) and preferred term (PT) and will be presented by descending order of frequency. AEs occurring before the first dose of study treatment will be summarized separately from new TEAEs occurring in the LTE. Listings will include all AEs (TEAEs and Non-TEAEs).

See Appendix 2. Partial Date Conventions for handling of partial dates for AEs for the purpose of assigning treatment-emergent flags. In the case where it is not possible to define an AE as treatment-emergent or not, the AE will be classified by the worst case, i.e. treatment emergent.

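### Rows 1 and 2 of the treatment-emergence table in both SAPs rule out pre-dose AEs without a severity check, contradicting the worsening limb of the TEAE definition

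*SAP*

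**What the plan says.** **Definition.** Protocol 8.3.4.1, SAP (Main Study) 19.1 and LTE SAP 18.1 each define a TEAE by two limbs: new onset after first dose, or worsening of something already there. The second limb reads "An AE that increases in severity after the initiation of olorinab, if the event was present at the time of treatment start" in the protocol, "An AE that increases in severity after the first dose of study treatment (olorinab or placebo), if the event was present" before first dose in the Main Study SAP, and "An AE that increases in severity after the first dose of LTE study treatment if the event was present before the dosing treatment" in the LTE SAP. Protocol 8.3.6 also asks that Main Study TEAEs which become more severe after the first LTE dose be summarised.

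**Algorithm.** Appendix 2 of each SAP contains a table headed as the algorithm for treatment emergence.

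- Row 1 takes a known start date with any stop date. The Main Study version is "If AE start date < study treatment first dose date, then not TEAE"; the LTE version substitutes the first LTE dose date.
- Row 2 of the Main Study table covers a start date described as "Partial, but known components show that it cannot be on or after date of first dose of study treatment". The result is not a TEAE, whatever the stop date.
- Row 2 of the LTE table gives the same result. Its condition, like that of row 3, refers to the first dose of study treatment, whereas the outcomes that compare dates in that table refer to the first LTE dose.

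No row in either table mentions severity.

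**Link between the two.** SAP 19.1 and LTE SAP 18.1 refer to Appendix 2 for handling partial AE dates, "for the purpose of assigning treatment-emergent flags". Where emergence cannot be determined, SAP 19.1 says "the AE will be classified by the worst case; i.e. treatment emergent"; LTE SAP 18.1 has the same rule.

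**The concern.** AEs are part of the primary endpoint of both the Main Study and the LTE, and most AE tables are restricted to TEAEs. If the table in Appendix 2 is what gets programmed, an AE recorded before first dose that rises from Grade 1 to Grade 3 on treatment is returned as not treatment-emergent, although the definition says the opposite.

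It would then be missing from the TEAE tables by system organ class and preferred term, by severity and by relationship, and from the tables of serious and fatal TEAEs and of study discontinuation. It would also be missing from the treatment-discontinuation table and its listing, both limited to TEAEs. In the LTE, the worsened Main Study TEAEs that protocol 8.3.6 asks for would not be flagged when their start date is known.

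**Working it through.** There is no plan figure to reproduce. The check sets the definition beside the table.

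**1. Main Study table.** Take an AE that starts before first dose and continues past it. Cross four kinds of start date with three kinds of stop date (known, partial, missing) and with worsening or not: 4 × 3 × 2 = 24 cases. The result does not depend on the kind of stop date.

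| Start date | Worsens: definition / table | Does not worsen: definition / table |
|---|---|---|
| Known (row 1) | TEAE / not | not / not |
| Partial, must precede dose (row 2) | TEAE / not | not / not |
| Partial, could be on or after dose | TEAE / TEAE | not / TEAE |
| Missing | TEAE / TEAE | not / TEAE |

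Rows 1 and 2 cover 2 × 3 = 6 date combinations. For a worsening AE, definition and table disagree in all 6; without worsening they agree in all 6. The last two lines over-include, in keeping with the worst-case rule. Worsened AEs are therefore lost only through rows 1 and 2, where the dates are best documented.

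**2. LTE table.** Row 1 names the first LTE dose and conflicts with LTE SAP 18.1 in the same way. Row 2 depends on how its condition is read. Read as the first LTE dose, it repeats the conflict. Read literally as the first Main Study dose, a partial-start AE that arose between the two first doses goes to row 3 and is judged by its stop date, so it is a TEAE if still ongoing at the LTE dose. Only AEs that began before the Main Study dose then fall under row 2, still without a severity check.

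**3. Does the recording practice matter?** Take an AE that starts on Day −5 at Grade 1, reaches Grade 3 on Day 10 and stops on Day 15.

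- One record, start Day −5: row 1 gives not a TEAE; the definition gives TEAE.
- Worsening entered as a new AE starting on Day 10: row 1 gives TEAE, as it should.

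The visible text supports either practice. Protocol 7.8.1.5 describes severity at onset and the maximum severity of the same AE. Protocol 7.8.1.1 lists worsening of a pre-existing condition as an AE in itself. Protocol 7.8.2.2 and SAP 19.1.2 name a single severity item, and 7.8.2.2 lists no date of severity change.

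**4. Size.** The documents give no AE counts. At the planned group sizes, one affected subject with no other TEAE in a category changes its incidence by:

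- single arm: 1/60 = 1.7 percentage points
- 25 and 50 mg pooled: 1/120 = 0.8
- all olorinab pooled: 1/180 = 0.6

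LTE group sizes are not given. Main Study AEs at risk start between consent and first dose: up to 14 + 19 = 33 days, or 28 + 19 = 47 days with biopsy. That is the length of a window, not a count of events.

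**5. A shortcut that fails.** Picking out worsened AEs by maximum grade above onset grade is not enough. An AE at Grade 3 on Day −20, Grade 1 by Day −1 and Grade 3 again on Day 10 has worsened after first dose, yet its maximum equals its onset grade.

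**The case against.** The strongest reply is that the appendix is titled as partial-date conventions, and that SAP 19.1 and LTE SAP 18.1 cite it only for partial dates. On that reading the table settles dates and the definition still supplies the severity limb. This is a fair reading and a programmer might follow it. But row 1 governs fully known dates, the table is headed as the algorithm for treatment emergence, and no precedence is stated. The worst-case rule does not help, because rows 1 and 2 give a definite answer. Nor is a deliberate narrowing documented: SAP 4.3 reports no change in definitions from the protocol, and LTE SAP 4.3 lists changes without this one.

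The second reply is that the consequence depends on AE-recording rules that are not in view. That stands. If each worsening gets its own record, no AE is misclassified by row 1.

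A reader might infer that worsened AEs disappear from the report. The documents do not support that. All AEs are listed; SAP 19.1 adds that "AEs occurring before the first dose of study treatment will be summarized separately"; the overall summary counts any AE, including those that are not TEAEs; and serious AEs have their own listing. A reader might also infer that the rule favours olorinab. The same rule applies in every arm, and nothing in the documents indicates a direction.

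**Conclusion.** The contradiction is real and can be read directly from the text: row 1 in both SAPs and row 2 in the Main Study SAP do not implement the worsening limb of the TEAE definition. LTE row 2 has the same gap, with the added ambiguity over which first dose it means. This should be fixed, because the TEAE flag feeds a primary safety endpoint.

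The practical effect rests on two conditions: that the table is programmed as written, and that a worsening stays on the original AE record. If both hold, the affected AEs are misclassified, not hidden. How many there are is unknown. The 1.7-point figure assumes 60 treated subjects per arm and an affected subject with no other TEAE in the category.

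**What to change.** In rows 1 and 2 of both tables, change the outcome to: *not TEAE, unless the AE was ongoing at the first (LTE) dose and its severity increased on or after that date (19.1/18.1), in which case TEAE*. In the LTE table, change the conditions of rows 2 and 3 to the first dose of LTE study treatment. Where the recorded data cannot show when an increase happened, apply the existing worst-case rule and footnote how many TEAEs enter that way. Do not rely only on maximum grade exceeding onset grade.

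Alternatively, if sites enter each worsening as a new AE with its own start date, say so in 19.1/18.1 and in Appendix 2 of both SAPs. The outcomes of rows 1 and 2 can then stay as they are.

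The text cost is one condition in two rows of each table plus the LTE wording, or a short statement in each SAP. The first route also needs confirmation that onset and maximum grade are held separately. Its downside is some over-counting. For example, an AE that started 70 days before the first LTE dose, peaked 60 days before it and is still ongoing would become a TEAE if the timing of its increase cannot be established. The footnote shows the extent of this but does not remove it.
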